### Goals

1. Identifying dynamic visual stimuli that are effective in manipulating arousal
2. Developing and testing the platform: integration of neurophysiologic, behavioral and visual stimulation components

### Equipment and instruments

1. Neurophysiologic assessment: EEG, GSR, EMG, ECG
2. Behavioral assessment: self-assessment manikin (SAM)
3. Visual stimulation: DVN presented on a display
4. Infrastructure: 2 laptops / PCs for rendering & processing of the data

### Conditions

1. Optimized visual stimulation (**OVS**)
2. Random visual stimulation control (**RVS**)

### Experiment structure

Stages of experiment:

1. Measuring temperature and a short COVID symptom questionnaire
2. Signing of informed consent
3. Urine drug test
4. Filling out the demographic questionnaire (5 minutes)
5. Filling out Perceived Stress Scale (Cohen, 1988)
6. Sensor setup (~30 minutes)
7. Sensor calibration (~5 minutes)
8. Instructions (~2 minutes)
9. Training block (~2.5 minutes)
- 10.25 Experimental blocks (~3 minutes per block). The blocks will be separated by breaks of 45 seconds.

## ***Approximate trial and block structure***

1. Fixation cross - 1 second.
2. Stimulation - 5 to 15 seconds total.
3. Behavioral response - 5 to 15 seconds.

## ***Data Analysis***

### *Optimization method*

In the optimization procedure, Dandelion Science defines the visual stimulation (VS) parameters and, while they are presented, monitor the response to them. Once the response is registered, we select the next set of parameters that is expected to achieve one or more of the following goals:

- identify and explore in detail VS parameters that affect a specific biomarker (i.e. that cause a significant shift in the biomarker in comparison with its baseline value);
- find the specific values for VS parameters that drive a combination of biomarkers to a predefined state (“target state”);
- improve our general predictive model of the relationship between VS parameters and bioresponse.

### *Effectiveness of DVN in controlling arousal*

Dandelion Science will also collect the responses to randomly chosen parameters. This data will be used to estimate the quality of the signal and variance in responses and serve as a prior distribution for the Bayesian model.

After we collect data for the baseline, we will compare the average response curve (a biomarker value for multiple participants over the course of random stimulation) with the response curve during the optimization procedure. We expect that after a few iterations, the biomarker values will diverge from the baseline. The required number of iterations to observe the effect is yet to be defined.

We want to test whether optimization leads to the gradual improvement in the ability of stimulation to cause change in arousal as registered by the biomarkers. To do so we will analyze how the biomarker changed with control stimulation (RVS) versus optimized stimulation (OVS). The divergence of the time series will be calculated using the ARIMA model, and the significance of the diversion will be assessed using the Chow Test.

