### ***Pilot***

To assess the effectiveness of the optimization process, a baseline response will be collected to serve as a control condition. Prior to the main experiment we will run a pilot experiment on 5 to 10 participants following the same structure as in the main experiment but with the visual stimulation parameters being chosen randomly during each iteration.

In addition, up to 5 participants will take part in pilot experiments with the cold pressor test (Lamotte et al., 2021), a simple and validated test that has been used in clinical and research settings to evaluate non-baroreflex-mediated sympathetic neural control in humans. During the test the subject immerses one hand or foot into ice water for up to 3 min while blood pressure and heart rate are monitored.

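### Experiment 1's averaged-curve Chow test specifies no participant baseline or participant effect, so a difference in starting level between random- and optimized-stimulation participants can pass for divergence

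*Combined protocol and SAP*

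**What the plan says.** Under Effectiveness of DVN in controlling arousal, the plan will "compare the average response curve (a biomarker value for multiple participants over the course of random stimulation" with the response curve during optimization. It adds that "we will analyze how the biomarker changed with control stimulation (RVS) versus optimized stimulation (OVS" and that "the significance of the diversion will be assessed using the Chow Test". No covariate, participant term or pre-stimulation value is named.

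The Pilot section says where the random-stimulation data come from: "we will run a pilot experiment on 5 to 10 participants following the same structure as in the main experiment", before the main experiment and with randomly chosen parameters. There, "a baseline response will be collected to serve as a control condition", so in that section the word baseline means the response to random stimulation and not a person's starting level.

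Three other places bear on the point:

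- Experiment 1, Conditions lists "Random visual stimulation control" beside OVS without saying whether the same people receive both.
- Experiment 1, Optimization method looks for stimulation parameters "that cause a significant shift in the biomarker in comparison with its baseline value", but does not define that value.
- Experiment 1, Experiment structure places "Sensor calibration (~5 minutes" before the training block and the 25 experimental blocks. The trial structure opens each trial with a 1-second fixation cross.

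**The concern.** EEG band power, skin-conductance peaks and heart-rate measures are likely to differ between people before any video is shown. An average over 5 to 10 people carries the average of their personal levels in every block. That offset is constant over the session, so it hardly affects block-to-block scatter, which is what the Chow test uses as its yardstick. The test therefore treats the offset as known far more precisely than it is.

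Aim 1 depends on this comparison. The question is whether the biomarker moves further under optimization than under random stimulation. A test that also responds to where two groups of people started can answer yes when optimization did nothing.

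**Working it through.** **Inputs.** From the documents: 25 blocks, 5 to 10 pilot participants, and up to 100 participants in Experiment 1. Assumed: 90 OVS participants (100 less 10), two-sided alpha 0.05, a linear trend, independent block errors, and a between-person share of variance (ICC) of 0.25 or 0.50. The documents give no alpha, power, effect size, SD, correlation or RVS/OVS split for Experiment 1, so there is no figure of the plan's own to reproduce.

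**1. Why the test rejects too often.** Set total variance to 1 and let each curve average n people over T = 25 blocks.

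- True variance of the difference in level between the curves: 2·ICC/n + 2(1 − ICC)/(nT).
- Variance the Chow test works with: 2(1 − ICC)/(nT).
- Ratio: 1 + T·ICC/(1 − ICC).

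At ICC 0.25 the ratio is 1 + 25 × 0.25/0.75 = 9.3. At ICC 0.50 it is 1 + 25 × 0.50/0.50 = 26. With equal groups n cancels, so recruiting more people does not cure the problem.

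**2. Size of the error.** Simulations had no true effect and used a Chow test on intercept and slope.

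| ICC | Averaged-curve Chow test | Participant-level comparison with baseline covariate |
|---|---|---|
| 0 | about 5% | about 5% |
| 0.25 | about 43–47% | about 4–6% |
| 0.50 | about 66–67% | about 4–6% |

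These rows are for 5 or 10 RVS against 90 OVS participants. Across repeated runs and other splits (10 against 10, 50 against 50) the Chow test's range was 42–48% at ICC 0.25 and 62–68% at ICC 0.50.

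**3. Subtracting one baseline value does not repair the averaged-curve test.** A single baseline as noisy as one block, subtracted from all 25 blocks, becomes a new constant offset. The ratio is 1 + 25(1 − ICC)/(1 − ICC) = 26 whatever the ICC, and the simulated rejection rate was about 64–68%. A less noisy baseline would do less harm.

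**4. What the covariate does for power.** This applies to a participant-level comparison. With 80% power unadjusted, adjusted power is Φ((1.960 + 0.842)/√(1 − ρ²) − 1.960), where ρ is the correlation between baseline and outcome.

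- ρ = 0.3: 2.802/0.954 = 2.937, power 83.6%.
- ρ = 0.5: 2.802/0.866 = 3.235, power 89.9%.
- ρ = 0.7: 2.802/0.714 = 3.923, power 97.5%.

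A simple change score replaces √(1 − ρ²) with √(2(1 − ρ)). At ρ = 0.5 that factor is 1, so power stays at 80%. At ρ = 0.3 it is 1.183, and power falls to Φ(2.802/1.183 − 1.960) = 65.8%.

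**The case against.** The strongest reply is that the plan is unspecified and not necessarily wrong. RVS is listed as a condition of Experiment 1, and the effectiveness section says responses to random parameters will also be collected. If each person receives both conditions and the comparison is made within person, stable differences cancel and the problem goes away. The plan also speaks of how the biomarker changed. If that means change measured afresh in every block from a pre-stimulation window, the simulated rejection rate returns to about 5–6%. An ARIMA model with differencing would also remove a constant offset, but the model order is not given. All of this stands as a reason to ask for clarification. None of it is written as the analysis, and the only fully random sessions described belong to the earlier pilot.

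A reader might also infer that the planned test loses about 10 to 12 points of power. The documents do not support that. Such a figure (80% rising to 89.9%, or 67.9% against an adjusted 80%) belongs to a participant-level covariate analysis at an assumed correlation of 0.5 and a reference power that Experiment 1 never states. For averaged curves under a Chow test, the main risk is false divergence.

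Nor do the documents show that the optimizer already uses each participant's own baseline and that the effectiveness test then discards it. The baseline value in the optimization section is undefined.

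**Conclusion.** The concern holds in this form. The stated effectiveness test has no participant-level baseline or participant effect. If the RVS and OVS curves come from different people, it can report a difference in starting level as an effect of optimization. That the values are unadjusted and the people different is the natural reading of the text, not something it states.

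Under the assumptions above, a nominal 5% test has a false-positive rate of roughly 45% with a quarter of the variance between people and about 67% with half. Independent errors, a linear trend and no differencing are assumed, so these figures show direction and rough size only. The gain in power from a baseline covariate (80% to about 84%, 90% or 98% at ρ of 0.3, 0.5 or 0.7) is a secondary benefit, measured against an unadjusted participant-level comparison.

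**What to change.** In Effectiveness of DVN in controlling arousal:

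1. State whether RVS and OVS are compared within or between participants.
2. Replace the averaged-curve Chow test with a participant-level model of the OVS-RVS difference in biomarker trajectory. Include a participant random effect and, as covariate, each participant's pre-stimulation value of the same biomarker. Base the conclusion on that difference.
3. Define the pre-stimulation value: either the recording made at calibration before any block, or the fixation periods before the first stimuli. One second is short for measures such as GSR peak counts or heart-rate variability, so the choice should suit the biomarker. Obtain it the same way in the pilot, which follows the same session structure.
4. Do not subtract a single baseline value and keep the averaged-curve Chow test.

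The cost is somewhat more analysis work, one degree of freedom and saving the pre-stimulation segment. The protocol does not say that biomarkers are recorded during calibration or that the participant is at rest then, so the sponsor should confirm that the segment is usable.

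### Experiment 1 tests OVS against RVS with a Chow test that has no participant-level error term, so the plan does not secure its type I error

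*Combined protocol and SAP*

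**What the plan says.** The comparison is set out in the combined protocol and SAP, Experiment 1, under *Effectiveness of DVN in controlling arousal*. The intention is to "compare the average response curve (a biomarker value for multiple participants over the course of random stimulation"). What it is set against is given only in these words: "with the response curve during the optimization procedure". The question is "whether optimization leads to the gradual improvement in the ability of stimulation to cause change in arousal". On method, "The divergence of the time series will be calculated using the ARIMA model". For inference, the section adds that "the significance of the diversion will be assessed using the Chow Test". The expected pattern is given as "We expect that after a few iterations, the biomarker values will diverge from the baseline", but "The required number of iterations to observe the effect is yet to be defined".

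The source of the RVS data is described in three ways:
- *Conditions* lists RVS beside OVS as a condition of the experiment.
- *Pilot* takes the control response from 5 to 10 people run before the main experiment with randomly chosen parameters.
- *Effectiveness of DVN in controlling arousal* also has random-parameter data "serve as a prior distribution for the Bayesian model".

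For this test the document names no unit of analysis, participant term, ARIMA order, break point, primary biomarker or alpha. The only stated type I error, 0.05 in *Optimization training and testing*, belongs to the matched-pairs VAS comparison. Experiment 1 aims at both raising and lowering arousal, and the test is given no direction.

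**The concern.** A standard Chow F test compares the residual sum of squares of a pooled fit with that of separate fits. Its error and degrees of freedom come from the points along the curves. Once participants are averaged, any difference between the people behind one curve and those behind the other becomes a difference between the curves, and nothing in the F ratio allows for it. The planned estimate of response variance is tied to signal quality and the Bayesian prior, not to this test.

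This is the only test stated for OVS against RVS on arousal, so it carries the significance statement for Aim 1. If the control curve comes from the pilot and the OVS curve from other people, a significant result could reflect who was in each group.

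**Working it through.** The plan gives no variance, alpha, sample size or power for this test, so there is no figure of its own to reproduce. The check asks how often the test rejects when OVS has no effect.

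**Inputs from the document.** There are 25 blocks (*Experiment structure*, item 10). A trial lasts 1+5+5 = 11 s to 1+15+15 = 31 s (*Approximate trial and block structure*), so a 180 s block holds 16 down to 5 trials and a session 25×5 = 125 to 25×16 = 400. A series of 25 points (per block) or 150 points (per trial) is therefore possible. The pilot has 5 to 10 people and Experiment 1 up to 100.

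**Assumptions.** Nominal 5%; split 10 RVS v 90 OVS; each person has a random level, a random linear drift over the session and AR(1) noise of SD 1 with correlation 0 or 0.3. Level and drift SDs are in noise units. None of these variances is in the document.

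**Mechanism.** Take uncorrelated noise and level differences only. The variance of the difference between two curve averages over T points is (1/n1 + 1/n2)(σ_b² + σ²/T). Time-point scatter implies (1/n1 + 1/n2)σ²/T. The ratio is 1 + Tσ_b²/σ²; sample size cancels and T does not. With σ_b = 0.5σ it is 1 + 25×0.25 = 7.25 at 25 points and 1 + 150×0.25 = 38.5 at 150.

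**Two-curve Chow F** (constant, trend and lag-1; different people; 25 points; 10 v 90; no effect):

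| Level SD, drift SD | Correlation 0 | Correlation 0.3 |
|---|---|---|
| 0, 0 | 4.3% | 5.1% |
| 0, 0.5 | 15.7% | 13.4% |
| 0.5, 0 | 32.5% | 23.8% |
| 0.5, 0.5 | 38.7% | 29.9% |
| 1, 1 | 66.3% | 55.8% |

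Repeat runs move the extremes by a point or two, hence about 14 to 68%. With both SDs 0.5, sample size makes little difference: 28.6 to 37.8% at 5 v 90 and 32.3 to 41.5% at 50 v 50. At 150 points the range is about 35 to 93%.

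**Cross-check.** A separate simulation set by intraclass correlation (ICC) agrees. A level SD of 0.5 is an ICC of 0.25/1.25 = 0.20. At that ICC, 25 points and correlation 0.3, rejection was 25.4% (10 v 10), 24.4% (10 v 90) and 25.1% (5 v 50).

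**Other readings, no effect:**
- 10-person RVS average v one OVS participant's curve: 13 to 67%.
- Different people, values referenced to each person's baseline: 9 to 44%.
- Same people supply both curves: 5 to 7%, or 10 to 12% if individual OVS response varies with SD 0.5.
- Chow break test on the OVS-minus-RVS series: about 4 to 8% at 25 points (about 10% when both SDs are 1). At 150 points it can reach about 39% without a trend term and is about 4 to 6% with one.

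**Participant as unit.** A Welch t-test on one slope per participant rejected 3 to 7% under the null.

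**The case against.** The strongest reply is that the document never says time points are the replicates, and that the large figures need three unstated conditions together: different people, a level-based model, and a test of equality between two curves. The Chow test is also a structural-break test, and the expectation of divergence after a few iterations is break language. On that reading a constant level difference between groups is not flagged, and the error rate at 25 points is close to nominal. Listing RVS as a condition also leaves room for the same people to receive both. All of this stands. It means the inflation belongs to particular implementations, although the separate pilot and the averaged RVS curve make the two-curve, different-people reading the natural one. The break reading is not a full escape either. With a trend term it treats a steady linear divergence as no break, yet gradual improvement is what the plan wants to detect. Without one, drift inflates it on a long series.

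A reader might infer that differencing the series would hide a real gradual effect. That is so for a differenced model with one lag and no moving-average term (no power for a 1 SD linear divergence at 10 v 90). With a moving-average term and a test of drift, power was 43 to 75% in small runs, some with convergence warnings. The inference does not hold for ARIMA models in general.

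A reader might also infer a familywise error across the biomarkers named in *Optimization training and testing*. Those features guide the optimizer; the document does not say that each is tested.

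Finally, Experiment 1 is development work. That lowers the stakes, but the plan still asks for a significance test.

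**Conclusion.** The point holds: the stated comparison has no participant-level error term, and the plan does not secure its type I error. On the two-curve, level-based reading with different people, false positives are about 14 to 68% at 25 points and higher at 150. Same-people data give about 5 to 12%, and the break reading runs from near nominal to about 39%. These percentages illustrate assumed variances, splits and model forms; they are not properties of the plan. The simulations also ignore the adaptive choice of stimuli.

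It is tempting to carry the error forward to the stimuli and pretrained model used in Experiment 2. The document does not support that: parameters are chosen by the optimizer, the model is pretrained on Experiment 1 data, and neither is made to depend on the Chow result. Pain success is judged separately by VAS. The consequence is limited to the Aim 1 arousal significance statement. The test should be respecified before the main experiment; confidence is medium because so much of its form is left open.

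**What to change.** Replace the Chow sentence with a participant-level comparison, for example:

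> For one primary arousal biomarker named before the main experiment, each participant contributes one prespecified summary over a fixed number of iterations: the slope on iteration, or the mean of later minus initial iterations. OVS is compared with RVS at a stated two-sided alpha, by Welch t-test if different participants supply the conditions or by paired t-test if the same participants do. Raise-target and lower-target stimulation are analysed separately, with alpha split between them. Other biomarkers are exploratory.

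State also whether RVS comes from the pilot, in which case the comparison is reported as non-randomized, or from a concurrent condition. If the optimizer carries learning from one participant to the next, include participant order. A within-person summary does not see that kind of improvement: with the OVS level rising by 1 SD across 90 participants and no within-session change, it rejected only about 5%.

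The change uses data already planned. Its cost is apparent power. With both SDs 0.5, 10 v 90 and a 0.5 SD linear effect, the slope test has 28 to 37% power against 62 to 75% for the two-curve Chow test, but the latter already rejects 30 to 39% with no effect. The summary must also suit the expected shape. For a 1 SD effect the slope has 76 to 91% power if the change is linear and 21 to 52% if it plateaus early. Later minus initial (last 15 minus first 3 blocks) has 58 to 73% and 57 to 97%. Splitting alpha by direction lowers power further.

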### ***Pilot***

To assess the effectiveness of the optimization process, a baseline response will be collected to serve as a control condition. Prior to the main experiment we will run a pilot experiment on 5 to 10 participants following the same structure as in the main experiment but with the visual stimulation parameters being chosen randomly during each iteration.

In addition, up to 5 participants will take part in pilot experiments with the cold pressor test (Lamotte et al., 2021), a simple and validated test that has been used in clinical and research settings to evaluate non-baroreflex-mediated sympathetic neural control in humans. During the test the subject immerses one hand or foot into ice water for up to 3 min while blood pressure and heart rate are monitored.

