## **CONSENT PROCESS**

All participants will be required to provide written informed consent for the planned research. Given that all participants are their own legal guardians, and no deception or blinding will occur in this research, it is expected that each participant will have full understanding of what they are agreeing to. As usual, participants will be informed that they can terminate participation at any time and for any reason, without negative repercussions and without having to state a reason. In addition, the participants will be provided with information regarding the funder of the study, the purpose of the study, expected length of participation, study procedures, participant responsibilities during the experiment, possible risks and discomforts, potential benefits from the research, and reimbursement of expenses (See attached the informed consent form).

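### The only control source described for Experiment 1 is an earlier, non-randomised pilot of 5 to 10 participants, so a cohort or period difference could be read as an effect of optimization

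*Combined protocol and SAP*

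**What the plan says.** All places are in the combined protocol and SAP, under Experiment 1 unless stated.

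- **Conditions** lists two conditions: OVS and "Random visual stimulation control" (RVS). It says nothing about how people or blocks are assigned to them.
- **Experiment structure** gives 25 experimental blocks per session, with no split between OVS and RVS.
- **Pilot** states where the control comes from: "a baseline response will be collected to serve as a control condition". The next sentence gives timing and size: "Prior to the main experiment we will run a pilot experiment on 5 to 10 participants". It then says how these sessions relate to the later ones: "following the same structure as in the main experiment but with the visual stimulation parameters being chosen randomly during each iteration".
- **Effectiveness of DVN in controlling arousal** says that "Dandelion Science will also collect the responses to randomly chosen parameters". These data also serve to estimate signal quality and variance and as the Bayesian prior. Once the baseline is in hand, the plan is to "compare the average response curve (a biomarker value for multiple participants over the course of random stimulation) with the response curve during the optimization procedure". RVS and OVS are then contrasted with an ARIMA model and a Chow test. No participant or cohort term is mentioned.
- **Consent Process** (study-wide) says that "no deception or blinding will occur in this research".

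**The concern.** Read together, these sections describe a historical control: a small group recorded first under random stimulation, then a larger group recorded later under optimized stimulation. The biomarkers that guide optimization (EEG alpha and beta bands, GSR peak counts, heart-rate variability, facial EMG) can differ between people and between recording periods for reasons unrelated to the clips. If every RVS recording comes from the earlier phase, condition and phase coincide, and no later analysis can separate them. This is a fault of the comparator. It would remain with a correct error term and with participant as the unit of analysis.

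What is at stake is Aim 1, the claim that visual stimuli can reliably modulate arousal, because this contrast is how the protocol tests whether optimization works.

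**Working it through.** **1. Is there a planned figure to reproduce?** No. Experiment 1 has no power or sample-size calculation, only a ceiling of 100 participants. The one calculation in the document (Optimization training and testing: 8 mm on the VAS, 30 participants, power 0.8) concerns pain ratings and does not bear on this point.

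**2. Is any concurrent or randomised control described?**

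| Question | What the documents give |
|---|---|
| Who supplies RVS data? | 5 to 10 pilot participants; no other number given |
| When? | Before the main experiment; no other time given |
| How is RVS or OVS assigned? | Not stated for people, blocks or trials |
| What is compared? | Averaged random-stimulation curve v curve during optimization |
| Adjustment for participant or phase? | None stated |

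**3. How large could the effect on the error rate be?** This is an illustration.

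Inputs from the documents: pilot n = 5 or 10; up to 100 participants in Experiment 1. Inputs assumed: the 100 include the pilot, giving 5 v 95 or 10 v 90; between-person SD = 1; no true optimization effect; a two-sided 5% participant-level test of mean level (the protocol states 0.05 only for the pain test); and a constant shift d between phases.

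Standard error of the difference, SE = √(1/n_RVS + 1/n_OVS):
- 5 v 95: √(1/5 + 1/95) = 0.459
- 10 v 90: √(1/10 + 1/90) = 0.333

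Rejection probability = P(Z > 1.96 − d/SE) + P(Z < −1.96 − d/SE).

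For d = 0.5:
- 5 v 95: d/SE = 1.089, so P(Z > 0.871) + P(Z < −3.049) ≈ 0.192 + 0.001 = 0.193
- 10 v 90: d/SE = 1.500, so P(Z > 0.460) + P(Z < −3.460) ≈ 0.323 + 0.000 = 0.323

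The range over assumed shifts is:

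| Assumed shift | 5 v 95 | 10 v 90 | Method |
|---|---|---|---|
| 0 | 5.0% | 5.0% | noncentral t |
| 0.25 SD | 8.4% | 11.5% | noncentral t |
| 0.3 SD | 10.0% | 14.7% | normal |
| 0.5 SD | 19.0% | 31.8% | noncentral t |

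The two methods agree at 0.5 SD to within a percentage point. The larger pilot has the higher rate, because a fixed bias is detected more reliably as the standard error falls. Neither a larger pilot nor more OVS participants removes the bias.

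**The case against.** The strongest reply has four parts.

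*RVS may also be recorded in the main experiment.* RVS is listed as a condition of Experiment 1, and the statement that random-parameter responses will also be collected is not limited to the pilot. This stands as far as it goes. A reader might infer that the pilot is certainly the only control, and the documents do not support that. It is the only source whose timing and size are described. If concurrent RVS is intended, its number and allocation are missing.

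*The pilot is matched to the main experiment, and its participants might return.* The Pilot section does say that the structure is the same. It does not say that the pilot participants are different people. That is the natural reading, since no second visit is described, but it is an inference. Returning participants would weaken the cohort part and leave the confounding with order and time. A reader might also infer a change of rig or staff from the Experiment 1 goal "Developing and testing the platform: integration of neurophysiologic, behavioral and visual stimulation components". That goal covers the experiment as a whole, and no section reports a change of equipment or personnel between the phases.

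*The hypothesis is gradual divergence, not a constant offset.* This stands against the illustration, which concerns mean level. It does not remove the problem. A Chow test compares the whole set of coefficients, so a difference in level alone can be significant unless the series are differenced, which is not stated. Cohorts or periods can also differ in slope, for example through habituation.

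*Experiment 1 is a development stage.* This stands, and it lowers the severity. The number of iterations is still open, and the only quantified success criterion is the VAS reduction in Study Endpoints, measured against no visual stimulation.

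**Conclusion.** The concern holds in a limited form. The one control source that the protocol describes for Experiment 1 is small, earlier and non-randomised. If the plan is followed as written, optimization is confounded with cohort and period. The difference could be read as an effect of optimization; the documents do not show that it would be.

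The figures of about 19% and 32% rest on an assumed 0.5 SD shift, a 5 v 95 or 10 v 90 split, no true effect and a test of mean level. They show sensitivity and are not estimates of this trial's error rate.

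Two stronger readings are not supported. First, a reader might infer that the bias passes into Experiment 2, whose Bayesian model is pretrained on Experiment 1 data. The protocol describes pretraining on those data, not on the OVS–RVS contrast, and the success of the stimuli in reducing pain is evaluated separately by VAS. Second, a reader might count the sampling error of a 5- or 10-person mean as a further bias. It is ordinary imprecision, already inside the SE above.

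This should be fixed before the main experiment starts, because the missing concurrent control cannot be recovered afterwards.

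**What to change.** Keep the pilot for signal quality and the Bayesian prior. Take the control for the OVS–RVS test from the main experiment, by one of two routes.

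1. **Preferred: randomise participants.** Assign a stated share of the already planned participants to full RVS sessions, run over the same period as the OVS sessions. This keeps a 25-block random-stimulation curve and avoids carry-over. The share also sets precision. With 100 people at 50:50, the difference in mean level detectable with 80% power (two-sided 5%) is (1.96 + 0.84) × √(1/50 + 1/50) = 0.56 SD. With 5 v 95 or 10 v 90 it is 1.29 or 0.93 SD.
2. **Alternative: randomise blocks.** Assign a fixed share of each participant's 25 blocks to RVS, at random positions. This controls for the person. However, arousal may carry over across the 45-second breaks, and a few scattered blocks do not give a full random-stimulation course.

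Under either route, specify a test of the condition-by-iteration difference with participant as the unit, for example a mixed model with participant effects. If RVS recording in the main experiment is already intended, state how many sessions or blocks and how they are assigned.

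Masking participants to clip type is a secondary, optional improvement, since the planned contrast uses physiological biomarkers. It would require a change to the Consent Process section.

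Cost: protocol wording and a randomisation list, with no extra participants or session time. The price is fewer optimization sessions under route 1. Under route 2 it is about 20% fewer optimization blocks if 5 of 25 are RVS (5/25 = 0.20).
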